8. STUDY PROCEDURES

8.1 Screening Procedures

Patients attending routine dental appointments who are identified by the Investigator as meeting all the inclusion / exclusion criteria, will be approached to discuss their possible participation in the study. Initial approach will be by the Dental Nurse to ask the patient and / or parent or guardian, if they would be interested in participating in the study. The study will be explained to them and each patient and / or parent or guardian will be given a copy / copies of the relevant Patient Information Sheet and Consent Forms to read and discuss with others if required. The patient and / or parent or guardian will be asked to confirm their interest in participating in the study by contacting the Dental Practice (no less than 24 hours after being given the Patient Information and Consent Form). They will be given the opportunity to discuss their participation in the study with the Investigator and ask any questions. If the patient and / or parent or guardian is still willing for the patient to participate in the study, they will be asked to return to the dental practice for Study Visit 1, when written Informed Consent will be taken by the Investigator. Patient availability for Study Visit 2 (7 to 14 days post-imaging) will also be checked.

The Site will document all patients and / or parent or guardian provided with the Patient Information Sheet and the outcome, (whether or not recruited to the study) on a Patient Screening / Recruitment Log.

8.2 Study Visit 1

At this visit, written Informed Consent (ref. 15.3) will be taken by the Investigator and the following information collected and procedures carried out.

Pre-Imaging Information collected

Demographics – DoB, ethnicity, relevant medical history and medications

Oral hygiene information - brushing regime, toothpaste and any other dental products used

Preparation of the Calcivis System

The Calcivis System must be prepared according to the manufacturer's Instructions For Use. Single-use Disclosing Solution (Photoprotein) should not be reconstituted more than 2 hours before the first tooth is imaged. Once reconstituted, the multi-use vial of Disclosing Solution (Photoprotein) should be stored at 2 to 80 C, up to a maximum of 4 weeks.

Preparation Procedures for Teeth

Relevant teeth will be identified and recorded for assessment using the Calcivis System as per Inclusion / Exclusion criteria.

All teeth surfaces to be imaged will be cleaned by the Dentist, by brushing with water or dental paste and rinsing with water and an air-water spray from a conventional dental 3-in-1 device, according to the Tooth Cleaning Protocol (Appendix 2). Patients will be asked to rinse out thoroughly with tap water.

Immediately following thorough air-drying of each tooth surface to be imaged, the Investigator will take a colour photograph with a standard intra-oral camera and record the ICDAS score /activity status.

Preparation Procedures for imaging with the Calcivis device

Care must be taken to ensure the surface of the tooth and surrounding area are free from saliva before imaging by the use of appropriate moisture control aids.

Each tooth will be air-dried for 5 to 10 seconds immediately before application of the disclosing solution and Calcivis System imaging.

Imaging with the Calcivis System

For teeth from each category (no lesions, and active lesions) a maximum of one tooth per patient can be imaged.

If a patient has more than one tooth of a particular category (sound tooth [no visible lesion], or tooth with active lesion) the investigator will use best clinical judgement to choose a tooth that most clearly fits the criteria of that particular population tooth type, for example if there is the choice of 2 teeth displaying lesions considered active, each identical except one of the teeth has a lesion in a plaque stagnation area (e.g. pits and fissures) and one more distant from plaque stagnation area, the tooth with the lesion in a plaque stagnation area will be chosen.

If the first image of a selected tooth is not clear for interpretation, it is acceptable to take a second image of that tooth, however no more than two images of any one tooth can be taken.

Recruitment will be stopped for each Investigator when a minimum of 17 evaluable images (as determined by the Investigators) from each tooth population have been obtained.

After all imaging has been completed, patients will be asked to rinse out with tap water.

Any adverse events observed or volunteered by the patient will be recorded. If appropriate a colour photograph will be taken of the adverse event with a standard intra-oral camera.

The images generated with the Calcivis System will be stored digitally on the laptop provided. The software will allow overlay of the two sets of images (before and after application of the disclosing solution) and interpretation of the resulting demineralization map of each imaged tooth will be carried out by the Investigator at the end of imaging.

At the end of the imaging procedures, the Investigator will share the images of the teeth with the patient.

The Calcivis System will be dismantled and cleaned according to the Instructions For Use. All consumables will be disposed according to the Instructions For Use.

Representatives of the Sponsor, Calcivis Ltd, will be available throughout Visit 1 to provide technical support for the use of the Calcivis System, as and when required. Consent will be sought from the patient and / or parent or guardian.

Post-Imaging Questionnaires / Visual Analogue Scales

At the end of the imaging procedures, patients will be asked to remain at the dental practice to complete a Patient Questionnaire / Visual Analogue Scale. Visit 1 is then complete.

In addition, at the end of each imaging study visit, the Investigator and Dental Nurse will each complete relevant sections of a User-Questionnaire

8.3 Study Visit 2 – 7 to 14 days post-imaging

At this visit, a final oral examination will be performed by the Investigator and any adverse events observed or volunteered by the patient will be recorded. If appropriate a colour photograph will be taken of the adverse event with a standard intra-oral camera.

8.4 Future Dental Care

Depending on the results, the Investigator may provide caries preventive advice to the patient and / or parent or guardian. The Investigator will not suggest further dental treatment based on the result of the images alone.

8.5 Independent Investigator Image Review

After all the images have been taken and verified as acceptable by the originating Investigator, and the CRFs collected, an independent review of the Calcivis images will be undertaken to assess the presence or absence of elevated luminescence on the surface to the teeth imaged with the Calcivis System.

This will be carried out by one of the other Investigators as follows:

Site	Original Investigator	Independent Investigator
1	[name]	[name]
1	[name]	[name]
3	[name]	[name]
3	[name]	[name]
5	[name]	[name]

The independent reviewer will be provided with evidence of both the original investigator's decision on tooth classification (i.e. no lesion, or active lesion, based on ICDAS coding / activity status) along with documented evidence of the clinician's intended location for assessment (this is all documented by the original Investigator prior to imaging using the Calcivis System). In addition, photographic evidence of the actual location of the luminescence will be provided. The determination by the independent reviewer will be made off-site, using the visible and Calcivis images along with copies of the original Investigator's documentation. The data from the independent reviewer will be used for the Primary analysis.

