In May 2014, the first formal Post-Approval Clinical Study was performed in adults (16 to 25 yrs old) using the advanced prototype Calcivis System. The Primary Objectives of the study were to assess the Performance and Safety of the Calcivis System, and the Secondary Objective was to assess user experience with the Calcivis System (both User and Patient). A total of 42 patients were recruited to the study from three UK, General Dental Practices, to obtain a total of 31 evaluable patients. Eligible patients were those with interpretable images of both a tooth with no visible lesion identified (ICDAS Code 0) and a tooth with a suspected visible lesion identified (ICDAS Code 1, 2 or 3). Images from 11 patients were not eligible for interpretation due to confounding factors including ambient light ingress, gross saliva contamination and poor disclosing solution coverage on the tooth surface. All these issues have been addressed in the design phase for the new commercial Calcivis System which is the subject of this study.

All 42 patients were included in the Safety Population – two adverse events were recorded – bleeding gums and slight gum abrasion – both were device-related, non-serious and asymptomatic to the patients with no action required. One other adverse event was recorded as a device deficiency when the device jammed and did not dispense fluid.

31 patients were included in the Agreement Population – analysis of the level of agreement between the ICDAS scores and elevated luminescence, (Y/N) as defined by the Investigators.

For the primary study objectives, the study results concluded that: -

1. The Calcivis System was safe in clinical use as determined by the low number and minor nature of the adverse events recorded.

2. Analysis of the overall level of agreement between elevated luminescence and the presence of lesions predicated as active by the Investigators showed agreement in 47 of the 65 teeth imaged (72.3 %) which was statistically significant, not due to chance and above the expected level of 70%.

(Of the 31 teeth identified by the Investigators with no visible lesions, 26 showed no elevated luminescence using the Calcivis System – corresponding to a negative percentage agreement of 83.9%. Of the 34 teeth with visible lesions identified by the Investigators, 21 showed elevated luminescence using the Calcivis System – corresponding to a positive percentage agreement of 61.8%).

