10. STATISTICAL ANALYSIS

10.1 Sample size

The study will assess the agreement between the Calcivis System and dentist rating of suitable teeth in two teeth populations: 'no visible lesions', and 'active lesions'. Based on previous study data and expert opinion, 'No visible lesions' are expected to correspond to 'no luminescence' according to the Calcivis system in at least 70% of cases. Similarly, 'active lesions' are also expected to correspond to 'luminescence' in at least 70% of cases.

Subjects will provide no more than one tooth of each tooth population. The study sample size is calculated in terms of the number of teeth of each tooth population required. The number of subjects required is then *at most* the total number of teeth required.

For the purpose of sample size calculations, the percentage agreement for each of the two tooth populations are jointly considered as measures of agreement. That is, the study will be deemed a success if the percentage agreement in both of the tooth status populations is statistically significant at the 2.5% level when compared to chance agreement (50%).

Expressed in terms of hypothesis tests, the null and alternative hypotheses are:

$$H_0: p_{a,i}=0.5 \text{ vs. } H_1: p_{a,i}>0.5 \text{ for each tooth status population } i$$

where $p_{a,i}$ is the percentage agreement in tooth status population i .

To achieve at least 90% power overall, a power of 94.9% has been used for each tooth status population individually. The planned method of analysis is an exact binomial test and this has been used to derive a required sample size of 81 for each of the tooth status populations. This is the first sample size after which all subsequent sample sizes provide at least 94.9% power.

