10.2 Statistical Analysis

General Considerations

The planned statistical analysis will be fully described in a Statistical Analysis Plan, which will be finalised prior to the locking of the study database. The main details of the planned analysis are described below.

The statistical analysis will be performed using SAS version 9.2 or higher.

All statistical tests will be conducted one-sided with a 2.5% level of significance and no adjustment will be made for multiple testing.

Analysis Populations

All patients on whom the Calcivis System is used will be included in the Safety Population.

The Agreement Population will include all teeth on which there is a dentist ICDAS score.

Analysis

The percentage agreement of the original dentist ICDAS score and the independent reviewer Calcivis finding ('no luminescence' or 'luminescence') will be presented along with an exact one-sided 97.5% confidence interval and p-value comparing the percentage agreement to 0.5 for the following:

- Teeth rated with 'no visible lesion' that are assessed as 'no luminescence' by the Calcivis System;
- Teeth rated with an 'active lesion' that are assessed as 'luminescence' by the Calcivis System.

The analysis of agreement will be performed on the Agreement Population.

The agreement between the original dentist ICDAS score and Calcivis finding will be analysed in the same manner.

User and patient questionnaire data and adverse events will be summarised descriptively for the Safety Population.

Missing Data

Missing data arising from teeth where the Calcivis System assessment is uninterpretable for reasons that are thought unrelated to the assessment outcome, will not be imputed. The reasons will be pre-defined in the Statistical Analysis Plan. Otherwise missing data will be considered as a disagreement in the calculation of agreement. Secondary analyses based on imputing all missing data as a disagreement will be conducted, if appropriate.

Otherwise missing data will not be imputed.

Interim Analysis

No interim analysis is planned for this study.

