## **11.0 Agreement**

The ICDAS defined tooth status (no visible lesions/active lesions) by the original Dentist, and the independent dentist assessment using the Calcivis System (no luminescence/luminescence) will be listed for each tooth.

A table will be presented cross-tabulating the original dentist ICDAS defined tooth status with the independent reviewer Calcivis finding.

Agreement between the ICDAS defined tooth status and Calcivis finding will be summarised using the negative and positive percent agreement as follows:

- The percentage of teeth with no visible lesion that are assessed as showing no luminescence by the Calcivis System (negative percent agreement);
- The percentage of teeth with an 'active lesion' that are assessed as showing

luminescence by the Calcivis System (positive percent agreement).

The hypothesis that agreement is greater than 0.5 will be tested using an exact binomial test and an exact one-sided 97.5% Clopper-Pearson confidence interval will be presented.

Secondary analyses based on imputing all missing data as a disagreement will be conducted, if appropriate.

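### The independent reviewer is handed the tooth classification before making the primary luminescence call that is scored against it: an avoidable departure from masked reading, probably of modest effect.

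*Protocol*

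**What the plan says.** Protocol 8.5 sets up a second reading of every Calcivis image by one of the other investigators, off-site. For that reading, "The independent reviewer will be provided with evidence of both the original investigator's decision on tooth classification", along with the location the first dentist intended to assess and photographic evidence of where the luminescence lies. The call is then made "using the visible and Calcivis images along with copies of the original Investigator's documentation". The section ends: "The data from the independent reviewer will be used for the Primary analysis". SAP 5.5 repeats the arrangement.

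Protocol 10.2 defines the primary statistic as "The percentage agreement of the original dentist ICDAS score and the independent reviewer Calcivis finding", calculated separately for teeth rated as having no visible lesion and teeth rated as having an active lesion. SAP 11.0 matches this: "A table will be presented cross-tabulating the original dentist ICDAS defined tooth status with the independent reviewer Calcivis finding". Under Protocol 10.1, "the study will be deemed a success if the percentage agreement in both of the tooth status populations is statistically significant".

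Protocol 10.2 adds one further agreement analysis: "The agreement between the original dentist ICDAS score and Calcivis finding will be analysed in the same manner". In context this is the original dentist's own reading of the images.

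**The concern.** The class given to the reviewer is the reference against which the reviewer's call is tested. Protocol 5.4 describes the luminescence map as something the dentist interprets, and neither document gives a numerical cut-off for elevated luminescence, so some images will need judgement. A reader who knows the class may settle unclear images in its favour. That would tend to raise negative and positive percent agreement together, and success requires both.

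The copied documentation may also contain the original investigator's own luminescence reading. Protocol 8.2 has that investigator interpret the map at the end of imaging, and Protocol 8.5 does not say which records are copied. If that reading is included, the second reading is not independent of the first.

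**Working it through.** **1. The plan's own figure.** Inputs from Protocol 10.1 and 10.2: exact binomial test, null agreement 0.50, expected agreement 0.70, one-sided 2.5%, at least 90% power for both tests jointly, hence √0.90 = 0.9487 per test (given as 94.9%). For each n, take the smallest r with P(X ≥ r | 0.50) ≤ 0.025; power is P(X ≥ r | 0.70). At n = 81, r = 50, attained alpha is 0.0224 and power is 0.957, or 0.957² = 0.916 jointly if the tests are independent. From n = 81 upwards, power stays at or above 0.9487 (checked to n = 200; the low point is 0.94886 at n = 85). The stated 81 is reproduced. Read literally, a threshold of 0.949 would give 86; the difference is rounding.

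**2. Is the reviewer masked anywhere?**
- Protocol 8.5 says the class and location are recorded before imaging. This protects the classification from the Calcivis image, not the reading from the classification.
- A different dentist reading off-site still holds the class.
- The additional analysis in Protocol 10.2 uses the reading of the dentist who classified the tooth, so it is not a masked check.
- The secondary analysis in SAP 11.0 concerns missing data only.

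**3. Does the reviewer need the class?** Protocol 5.3 describes site-specific use in this study. That is a reason to supply the intended location; it does not require the ICDAS code or activity status.

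**4. How much does the written class add?** Under Protocol 7.4 a sound tooth is a canine or incisor coded ICDAS 0, and a lesion tooth is a molar or premolar with a visible lesion coded 2 or 3. Protocol 8.2 images only these two categories. The mock-up of SAP Listing 9 shows the same split: buccal, code 0, against occlusal, code 2 or 3. A dentist who sees an eligible tooth can largely infer its class.

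**5. Illustration of a pull towards the known class.** Let b be the share of true disagreements read as agreement. The documents give no value, so b is assumed. Apparent agreement is p + b(1 − p). Every n from 81 (required) to 90 (the maximum per population in the synopsis) was computed with its own critical value, for example 50/81, 53/85 and 55/90. At p = 0.50, the expected number of teeth changed is 0.5 × n × b.

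| b | Teeth changed | One test passes, p = 0.50 | Both pass, both p = 0.50, independent | One test passes, p = 0.70 |
|---|---|---|---|---|
| 0 | 0 | 1.5–2.4% | 0.02–0.06% | 94.9–97.3% |
| 5% | 2.0–2.3 | 4.3–6.3% | 0.2–0.4% | 97.4–98.8% |
| 10% | 4.1–4.5 | 10.4–14.5% | 1.1–2.1% | 98.8–99.5% |

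If one population is truly at 50% and the other at 83.9% (the negative agreement in the earlier study, Protocol 5.7), the second test passes almost surely. The chance of passing both then equals the one-test rate in the third column.

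**The case against.** The strongest objection is step 4: the written class tells the reader little that the tooth does not. This largely stands. It means that withholding the class removes only part of the reader's expectation, and that the table in step 5 cannot be credited to the documents handed over. It does not justify supplying the reference answer as well, and it does not cover a possible first luminescence reading, which tooth type cannot reveal.

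A second objection concerns direction. The reviewer receives both the intended location and evidence of where the luminescence lies, which suggests a check that the two match. Rejecting off-site luminescence on a lesion tooth would lower positive agreement, so the net direction in that test is not certain. This stands as a qualification; the effect comes from knowing the location rather than the class.

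Third, the larger false-positive rates need particular conditions. With both populations at 50%, joint false success stays at or below 2.1% even at b = 10%. At the planned 70% agreement, power is already 95–97% and a pull changes the outcome little. Both statements are correct.

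A reader might go further and infer that the study's false-positive rate really is 4–6% or 10–14%, or that the primary result would be invalid. The documents support neither: the shares are assumed, and nothing in them measures how far the disclosure moves a reading.

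**Conclusion.** The plan discloses the reference classification, and possibly the first luminescence reading, to the person making the only reading used in the primary analysis. This is an avoidable departure from a masked, independent reading and should be corrected. The probable direction is towards agreement. The size is unknown and probably modest, because tooth type and the visible lesion largely reveal the class, and off-site rejection may work the other way in the lesion teeth.

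The false-positive rates of 4–6% and 10–14% rest on assumed pulls of 5% and 10% and true agreement of 50%. They describe reader expectation from any source, not the bias that the change would remove. It should also not be assumed that the reviewer will see the first dentist's luminescence call: the documents leave that open.

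**What to change.** Amend Protocol 8.5 and SAP 5.5 as follows.

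- Give the reviewer coded images in shuffled order, with the intended location only, taken from the pre-imaging record.
- Withhold the written classification, ICDAS code, activity status and any luminescence reading by the original investigator until the reviewer's call is locked. If the photographic evidence of luminescence location carries that investigator's mark or call, treat it as such a reading.
- Keep the outcome unchanged: presence or absence of elevated luminescence on the imaged surface, with the intended location used as now. Narrowing it to a call at a marked point could redefine the endpoint.
- Use the locked call for the primary analysis.
- State in the SAP and the study report that masking is only partial, because tooth type and lesion remain visible.

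The cost is wording in two sections and a small amount of administration to code, mark and shuffle files for 170 to 180 teeth (2 × 85 to 2 × 90) and to log the lock. No further reader, visit or image is needed, and the requirement stays at 81 teeth per population. Some unmasking will remain.

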9. ADVERSE EVENTS

9.1 Definitions

Adverse Event (AE) – any untoward medical occurrence, unintended disease or injury, or untoward clinical signs (including abnormal laboratory findings) in subjects, users or other persons, whether or not related to the investigational medical device.

This definition includes events related to the investigational device and comparator and events related to the procedures involved.

For users or other persons, this definition is restricted to events related to the investigational medical devices.

A Serious Adverse Event (SAE) – is an adverse event that –

- Led to death
- Led to a serious deterioration in the health of a subject that –
 - resulted in a life-threatening illness or injury
 - resulted in a permanent impairment of a body structure or a body function
 - required in-patient hospitalization or prolongation of existing hospitalization
 - resulted in medical or surgical intervention to prevent a permanent impairment of a body structure or a body function
- Led to foetal distress, foetal death or a congenital abnormality or birth defect

Planned hospitalisation for a pre-existing condition, or a procedure required by the CIP, without serious deterioration in health, is not considered a serious adverse event

Adverse Device Effect (ADE) – an adverse event related to the use of an investigational medical device.

This definition includes any events resulting from insufficient or inadequate instructions for use, deployment, implantation, installation, or operation, or any malfunction of the investigational device.

This definition also includes any event resulting from user error or form intentional misuse of the investigational device.

Serious Adverse Device Effect (SADE) – adverse device effect that has resulted in any of the consequences characteristic of a serious adverse event.

Anticipated Serious Adverse Device Effect (ASADE) - an effect which by its nature, incidence, severity or outcome has been identified in the risk analysis report

Unanticipated Serious Adverse Device Effect (USADE) - serious adverse device effect which by its nature, incidence, severity or outcome has not been identified in the current version of the risk report.

Device Deficiency – inadequacy of a medical device with respect to its identity, quality, durability, reliability, safety or performance.

Device deficiencies include malfunctions, use errors and inadequate labelling.

Device deficiencies which result in SADEs or USADEs, will be managed as detailed below.

Device deficiencies that did not lead to an adverse event, but could have led to a medical occurrence if suitable action had not been taken, or intervention had not been made or if circumstances had been less fortunate will also be managed as detailed below.

Use error – act or omission of an act that results in a different medical device response than intended by the manufacturer or expected by the user.

Use error includes slips, lapses and mistakes.

An unexpected physiological response of the subject does not itself constitute a use error.

Severity Definitions – the following definitions will be used to determine the severity rating for all SAEs

- Mild – awareness of signs or symptoms, that does not interfere with the subject's usual activity, or is transient which resolves without treatment and with no sequelae
- Moderate – a sign or symptom which interferes with the subject's usual activity
- Severe – incapacity with inability to do work or usual activities

